[figure not shown]

Protocol for non-interventional studies based on existing data

Document Number:	c09038525-01
BI Study Number:	1200.270
BI Investigational Product:	Gi(l)otrif [®] (afatinib)
Title:	RealGiDo: Real-world data on Gi(l)otrif [®] dose adjustment in first-line treatment, TKI-naïve, advanced non-small cell lung cancer patients with EGFR activating mutations
Brief lay title:	Real World Data on Gi(l)otrif [®] dose adjustment
Protocol version identifier:	1.0
Date of last version of protocol:	01 March 2016
PASS:	No
EU PAS register number:	EU PAS register number not yet assigned as the study is not yet registered in the EU PAS Register. The study will be registered shortly before the start of data collection.
Active substance:	afatinib Antineoplastic agents, tyrosine kinase inhibitors ATC code: L01XE13
Medicinal product:	Gi(l)otrif [®] 50mg, 40mg, 30mg, 20mg tablet
Product reference:	20mg: EU/1/13/879/001, EU/1/13/879/002, EU/1/13/879/003 30mg: EU/1/13/879/004, EU/1/13/879/005, EU/1/13/879/006 40mg: EU/1/13/879/007, EU/1/13/879/008, EU/1/13/879/009 50mg: EU/1/13/879/010, EU/1/13/879/011, EU/1/13/879/012
Procedure number:	EMA/H/C/002280
Joint PASS:	No
Research question and objectives:	
Primary objective: To assess the effects of Gi(l)otrif[®] dose modification on the frequency and severity of adverse drug reactions, time on treatment and time to progression with Gi(l)otrif[®] in real-world setting and compare with data from Lux-Lung 3 trial in a descriptive manner.
 
Secondary objective: To obtain information on frequency and reasons for a modified starting dose of Gi(l)otrif[®] in real-world setting

Protocol for non-interventional studies based on existing data

BI Study Number 1200.270**c09038525-01**

Proprietary confidential information © 2016 Boehringer Ingelheim International GmbH or one or more of its affiliated companies

Countries of study:	Austria, Canada, France, Germany, Italy, Japan, Korea, Mexico, Poland, Singapore, Spain, Taiwan, US
Author:	 Phone:  Fax:  E-mail: 
Marketing authorisation holder:	Boehringer Ingelheim International GmbH [name] Germany
Date:	01 March 2016

Page 1 of 38**Proprietary confidential information****© 2016 Boehringer Ingelheim International GmbH or one or more of its affiliated companies. All rights reserved.**
This document may not - in full or in part - be passed on, reproduced, published or otherwise used without prior written permission

2. LIST OF ABBREVIATIONS

ADR	Adverse Drug Reaction
AE	Adverse Event
AESI	Adverse Event of Special Interest
ASCO	American Society of Clinical Oncology
AUC	Area under the Curve
BI	Boehringer Ingelheim
CA	Competent Authority
CI	Confidence Interval
CML	Local Clinical Monitor
CRA	Clinical Research Associate
CRO	Clinical Research Organization
eCRF	Electronic Case Report Form
CTCAE	Common Terminology Criteria for Adverse Events
CTMF	Clinical Trial Master File
CTP	Clinical Trial Protocol
CTR	Clinical Trial Report
Del19	EGFR Exon 19 Deletion
ECOG	Eastern Cooperative Oncology Group
eCRF	Electronic Case Report Form
EDC	Electronic Data Capture
EGFR	Epidermal Growth Factor Receptor
EGFRm+	Epidermal Growth Factor Receptor Mutation Positive
ErbB	Erythroblastic Leukemia Viral Oncogene Homolog
EU	European Union
FDA	Food Drug Administration
GCP	Good Clinical Practice
GEP	Good Epidemiological Practice
GPP	Good Pharmacoepidemiology Practice
HER2	Human Epidermal Growth Factor Receptor 2
HR	Hazard Ratio
ICH GCP	International Conference on Harmonisation guideline for Good Clinical Practice
IEC	Independent Ethics Committee
IRB	Institutional Review Board
ISF	Investigator Site File
L858R	L858R mutation at EGFR exon 21
LUX-Lung 3	BI Trial No.1200.32
MAH	Marketing Authorization Holder
NIS	Non-Interventional Study
NISed	Non-Interventional Study based on existing data
NSCLC	Non-Small Cell Lung Cancer
OPU	Operative Unit
OS	Overall Survival
PFS	Progression Free Survival
PK	Pharmacokinetics

PRO	Patients Reported Outcome
RDC	Remote Data Capture
RWD	Real World Data
SADR	Serious Adverse Drug Reaction
SAE	Serious Adverse Event
SD	Standard Deviation
SDV	Source Data Verification
SEAP	Statistical and Epidemiological Analysis Plan
SOP	Standard Operating Procedure
SUSAR	Suspected Unexpected Serious Adverse Reaction
TCM	Trial Clinical Monitor
TKI	Tyrosine Kinase Inhibitor
TMF	Trial Master File

3. RESPONSIBLE PARTIES

Boehringer Ingelheim (BI) has appointed a Trial Clinical Monitor (TCM), responsible for coordinating all required activities, in order to

- Manage the study in accordance with applicable regulations and internal standard operating procedures (SOPs),
- Direct the study team in the preparation, conduct, and reporting of the study,
- Ensure appropriate training and information of Local Clinical Monitors (CMLs), Clinical Research Associate (CRAs), and investigators of participating countries.

Data Management and Statistical Evaluation will be done by BI according to BI SOPs.

The organization of the study in the participating countries will be done by the respective local BI-operative unit (OPU) or by a Contract Research Organization (CRO) with which the responsibilities and tasks will have been agreed and a written contract filed before initiation of the study. In each local BI OPU participating in this study, a CML will be appointed responsible for coordinating the activities required in order to manage the study in accordance with applicable regulations and internal SOPs in the countries covered by the respective BI OPU. On-site monitoring will be performed by BI or a CRO appointed by BI.

An Investigator Site File (ISF) containing all relevant study related documentation will be maintained according to local regulations and BI SOPs at each study site. A copy of the ISF documents will also be kept as an electronic Trial Master File (TMF) at BI according to BI SOPs. Documents related to participating investigators and other important participants, especially their curricula vitae, will be filed in the TMF.

The coordinating investigator who will sign the report of this non-interventional study has been appointed by BI. The coordinating investigator has experience in lung cancer studies.

Co-ordinating investigator:

[REDACTED]

Phone: [REDACTED]

4. ABSTRACT

Name of company: Boehringer Ingelheim			
Name of finished medicinal product: Gi(1)otrif®			
Name of active ingredient: afatinib Antineoplastic agents, tyrosine kinase inhibitors ATC code: L01XE13			
Protocol date: 01 March 2016	Study number: 1200.270	Version/Revision: 1.0	Version/Revision date:
Title of study:	RealGiDo: Real-world data on Gi(1)otrif® dose adjustment in first-line treatment, TKI-naïve, advanced non-small cell lung cancer patients with EGFR activating mutations		
Rationale and background:	
Post-hoc analyses from LUX-Lung 3 suggest that tolerability-guided dose adjustment of afatinib is an effective measure to reduce treatment-related AEs without affecting therapeutic efficacy.
 
The objective of this non-interventional study (NIS):
 
Real-World Data will help to understand if dose modifications are done similar as in LUX-Lung 3 trial and if the outcome on safety and effectiveness are as in trial settings. Furthermore, data on modified starting doses, the underlying reasons and effects on safety and outcome will be collected.
		
Research question and objectives:	
Primary objective:
 
To assess the effects of Gi(1)otrif® dose modification on the frequency and severity of adverse drug reactions, time on treatment and time to progression with Gi(1)otrif® in real-world setting and compare with data from LUX-Lung 3 trial in a descriptive manner.
 
Secondary objective:
 
To obtain information on frequency and reasons for a modified starting dose of Gi(1)otrif® in real-world setting.
		
Study design:	Non-interventional, multi-country, multi-site study based on existing data from medical records of patients treated with Gi(1)otrif® as part of the routine treatment according to the approved label.		
Population:	
Sites in countries with launch dates prior to 1st Jan 2015 and known to prescribe Gi(1)otrif® on a regular basis will be chosen.
 
In/-Exclusion criteria:
		

Protocol for non-interventional studies based on existing data

BI Study Number 1200.270**c09038525-01**

Proprietary confidential information © 2016 Boehringer Ingelheim International GmbH or one or more of its affiliated companies

	
 1. EGFR mutated (common mutations), TKI-naïve advanced NSCLC treated with Gi(1)otrif[®] as the first-line treatment for NSCLC within the approved label will be included 2. Patients treated within clinical trials are excluded 3. Patients still on treatment with Gi(1)otrif[®] will be excluded unless treatment period is ≥ 6 months
Variables:	
Primary outcomes:
 
Safety outcomes:
 
Percentage of subjects with adverse drug reactions by severity class
 
Effectiveness outcomes:
 
Time on treatment with Gi(1)otrif[®]
 
Time to progression with Gi(1)otrif[®]

Data sources:	NIS based on existing data from medical records of patients.
Study size:	At least 200 patients. ≥ 200 patients are planned based on feasibility aspects and assumptions.
Data analysis:	
Safety data will be analysed in a descriptive manner. Incidence and severity of adverse drug reactions will be summarized and displayed. For patients who have dose modifications, frequency and severity of the most common AEs pre- and post-dose modification will be summarized and displayed.
 
For effectiveness analysis, both time on treatment and time to progression will be estimated using Kaplan-Meier method, and the median along with two-sided 95% CI will be displayed (use the Greenwood's formula for estimation of standard errors). Log-rank test will be applied to compare between patients with and without dose modifications.

Milestones:	
Start of data collection in May 2016
 
End of data collection in December 2016
 
Final report of study results expected in March 2017

5. AMENDMENTS AND UPDATES

Not applicable.

6. MILESTONES

Milestone	Planned Date
Registration in the European Union (EU) Post-Authorization Studies (PAS) register	EU PAS register number not yet assigned as the study is not yet registered in the EU PAS Register. The study will be registered shortly before the start of data collection.
Start of data collection	31 May 2016
End of data collection	31 Dec 2016
Final report of study results:	31 Mar 2017

7. RATIONALE AND BACKGROUND

The first marketing approval of afatinib was granted on 12 Jul 2013 in the USA (trade name Gilotrif[®]) for the indication of first-line treatment of patients with metastatic non-small cell lung cancer (NSCLC) whose tumors have epidermal growth factor receptor (EGFR) exon 19 deletions or exon 21 (L858R) substitution mutations as detected by an FDA-approved test. It was approved in the European Union on 25 Sep 2013 (trade name Giotrif[®]) as monotherapy indicated for the treatment of EGFR TKI-naïve adult patients with locally advanced or metastatic NSCLC with activating EGFR mutation(s). [REDACTED]

The approval of Giotrif[®] was based on the results observed in the pivotal trial LUX-Lung 3 study. The LUX-Lung 3 study investigated the efficacy of chemotherapy compared with afatinib, a selective, orally bioavailable ErbB family blocker that irreversibly blocks signaling from epidermal growth factor receptor (EGFR/ErbB1), human epidermal growth factor receptor 2 (HER2/ErbB2), and ErbB4 and has wide-spectrum preclinical activity against EGFR mutations. A total of 1,269 patients were screened, and 345 were randomly assigned to treatment (afatinib or chemotherapy). Median progression-free survival (PFS) was 11.1 months for afatinib and 6.9 months for chemotherapy (hazard ratio [HR], 0.58; 95% CI, 0.43 to 0.78; P=.001). Median PFS among those with exon 19 deletions and L858R EGFR mutations (n=308) was 13.6 months for afatinib and 6.9 months for chemotherapy (HR, 0.47; 95% CI, 0.34 to 0.65; P=.001). The most common treatment related adverse events were diarrhea, rash/acne, and stomatitis for afatinib and nausea, fatigue, and decreased appetite for chemotherapy. Patients reported outcomes (PROs) favored afatinib, with better control of cough, dyspnea, and pain ([P13-07382](#)).

Afatinib 40 mg/day (oral) is approved for the treatment of patients with advanced EGFRm+ NSCLC. Dose adjustments are recommended based on pre-defined tolerability criteria. A post-hoc analyses of the effects of afatinib dose reduction on adverse events (AEs), pharmacokinetics (PK) and PFS in the phase III LUX-Lung 3 trial showed that dose reductions occurred in 53% (122/229) of patients; the majority (86%) within the first 6 months of treatment. In patients who dose reduced, decreases in the incidences of drug-related all grade (grade \geq 3) AEs were 99.2% (20.5%) to 46.7% (4.1%) for diarrhea, 88.5% (26.2%) to 38.5% (3.3%) for rash/acne, 77.0% (12.3%) to 27.9% (0%) for stomatitis, and 44.3% (16.4%) to 36.9% (4.9%) for nail effects. Dose reductions tended to be more common in female patients, older patients, patients of Eastern Asian ethnicity, and patients with lower body weight. Dose reduction was more likely in patients with higher plasma concentrations of afatinib. On Day 43, patients who dose reduced to 30 mg \geq 4 days previously (n=38) had geometric mean plasma afatinib concentrations of 24.4 ng/mL, vs 23.7 ng/mL in patients who remained on the 40 mg dose (n=126). Median PFS was 11.3 months in patients who dose reduced during the first 6 months of treatment, vs 11.0 months in patients who did not (HR=1.25 [95% CI, 0.91–1.72]). [ASCO 2015, Yang et al, # 8073] ([P15-05676](#)).

Post-hoc analyses from LUX-Lung 3 suggest that tolerability-guided dose adjustment of afatinib is an effective measure to reduce treatment-related AEs without affecting therapeutic efficacy:

- The frequency and severity of treatment-related AEs was lower following dose reduction
- Tolerability-guided dose modification reduced the inter-patient variability of afatinib exposure, while maintaining efficacious plasma levels
- Efficacy outcomes were similar in patients who dose reduced due to AEs versus those who did not

This real-world data (RWD) study will help to understand if dose modifications are done similar as in LUX-Lung 3 trial and if the outcome on safety and effectiveness are as in trial settings.

8. RESEARCH QUESTION AND OBJECTIVES

Research objective:

Data from real-world will help to understand if dose modifications are done similar as in LUX-Lung 3 trial and if the outcome on safety and effectiveness are as in trial settings. Furthermore, data on modified starting doses, the underlying reasons and effects on safety and outcome are needed.

Primary objective:

To assess the effects of Gi(1)otrif[®] dose modification on the frequency and severity of adverse drug reactions (ADRs), time on treatment and time to progression with Gi(1)otrif[®] in real-world setting and compare with data from LUX-Lung 3 trial in a descriptive manner.

Secondary objective:

To obtain information on frequency and reasons for a modified starting dose of Gi(1)otrif[®] in real-world setting.

9. RESEARCH METHODS

9.1 STUDY DESIGN

This is a non-interventional, multi-country, multi-site study based on existing data from medical records of patients treated with Gi(l)otrif[®] as part of the routine treatment according to the approved label.

Key study outcomes are:

- Effects of Gi(l)otrif[®] dose reduction on frequency of ADRs, and time on treatment, time to progression
- Proportion of patients starting with modified Gi(l)otrif[®] dose and the underlying reason(s)

Data on diagnosis, gender, date of birth, ethnicity, body weight and height, Eastern Cooperative Oncology Group performance score (ECOG) ([R14-0080](#)), EGFR mutational subgroup (Del19/L858R), starting dose of Gi(l)otrif[®], start date of Gi(l)otrif[®] treatment, dose modifications with date, ADRs, concomitant medications (limited to medication for management of diarrhea, skin effects, mucositis/stomatitis as dichotomous variables (e.g. received anti-diarrhea medication yes/no), reason for dose modification of Gi(l)otrif[®], treatment duration of Gi(l)otrif[®], time to progression and type of progression (clinical, radiographic or both clinical/radiographic progression) will be collected from patients medical records by investigators.

9.2 SETTING

The NIS will be conducted in about 25-30 sites globally which are experienced in lung cancer treatment. An average of 8-10 patients per site (with a maximum of up to 15 patients per site) is expected.

Patient participation in this NIS is voluntary. Patients were treated and are treated according to the standard of care independent of patient's consent to participate in this NIS.

9.2.1 Selection of study population

Site selection:

Sites in countries with launch dates prior to 1st Jan 2015 and known to prescribe Gi(l)otrif[®] on a regular basis will be chosen. Asian and Non-Asian countries will be included.

Inclusion criteria:

All consecutive patients will be included if all the following criteria are present:

- Age \geq 18 years

Protocol for non-interventional studies based on existing data

BI Study Number 1200.270

c09038525-01

Proprietary confidential information © 2016 Boehringer Ingelheim International GmbH or one or more of its affiliated companies

- Patients with EGFR mutation (common mutations), TKI-naïve advanced NSCLC, treated with Gi(l)otrif[®] as the first-line treatment for NSCLC within the approved label
- Signed and dated written informed consent per regulations. (Exemption of a written informed consent for retrospective observational studies in some countries per local regulations and legal requirements.)

Exclusion criteria:

Patient won't be included if any of the following criteria is present:

- Any contraindication to Gi(l)otrif[®] as specified in label.
- Patients with uncommon mutations are excluded as uncommon mutations are not within label in all participating countries (e.g. USA).
- Patients still on treatment with Gi(l)otrif[®] will be excluded unless treatment period is ≥ 6 months.
- Patients treated with Gi(l)otrif[®] within an interventional trial.

A log of all patients included into the study will be maintained in the ISF at the investigational site.

Patients treated with Gi(l)otrif[®] in interventional trials are excluded to ensure the non-interventional setting of this study. The threshold of ≥ 6 months treatment with Gi(l)otrif[®] for patients being still on treatment was chosen to avoid early censoring and enable collection of mature data on ADRs and treatment duration. However, patients who stopped Gi(l)otrif[®] < 6 months will be included to avoid bias. All patients fulfilling inclusion and exclusion criteria from a site will be entered to avoid bias. The maximum of 15 patients per site was chosen to avoid bias by high proportion of patients coming from one site.

BI reserves the right to discontinue the study overall or at a particular study site at any time for the following reasons:

1. Failure to meet expected enrolment goals overall or at a particular study site.
2. Violation of Good Clinical Practice (GCP) (as applicable), the Study Protocol, or the contract by a study site or investigator, disturbing the appropriate conduct of the study.

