9.7 DATA ANALYSIS

9.7.1 Main analysis

All collected data will be analysed separately for patients starting with 40mg and \leq 30mg. Although due to anticipated low sample size in patients starting with \leq 30mg, it will be mainly for exploratory purpose. Baseline demographics will be analysed with descriptive statistics (N, median, mean, 25%, 75% percentile, SD) and compared descriptively between patients who have dose modifications within the first 6 months of Gi(l)otrif[®] treatment and those who do not. All the demographics, safety and efficacy data from this study in real-world setting will be compared with data from LUX-Lung 3 trial in descriptive manner.

Analysis of Safety:

[figure not shown]
Safety analysis will include all patients treated with Gi(l)otrif[®] and be descriptive in nature. Incidence and severity of ADRs according to Common Terminology Criteria for Adverse Events (CTCAE) criteria (version 4.0) ([R15-5988](#)) when available will be summarized and displayed in number/percentage. For patients who had Gi(l)otrif[®] dose modifications within the first 6 months of Gi(l)otrif[®] treatment, frequency and severity of the common ADRs pre- and post-dose modification will be analysed (\geq 40mg vs $<$ 40mg; and \geq 30mg vs $<$ 30mg). Missing or incomplete ADR dates will be imputed according to BI internal SOPs.

Analysis of Effectiveness:

Effectiveness analysis will include all patients treated with Gi(l)otrif[®]. Time on treatment is from the date of first dose of Gi(l)otrif[®] treatment to the date of last dose of Gi(l)otrif[®] treatment. Time to progression is from the date of first dose of Gi(l)otrif[®] treatment to the earliest date of documented progression (clinical, radiographic or both clinical/radiographic progression) or death. Time on treatment and time to progression will be estimated using Kaplan-Meier method, and the median along with two-sided 95% CI will be displayed (use the Greenwood's formula for estimation of standard errors). Log-rank test will be applied to compare between patients with and without dose modifications. Time on treatment and time to progression will be compared between patients who dose reduced to $<$ 40 mg within the first 6 months of Gi(l)otrif[®] treatment and those who remained on Gi(l)otrif[®] 40 mg once daily. This is in analogy to the analysis made on LUX-Lung 3 where a cut-off of 6 months was used as most dose reductions occur during this time.

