In the analyses of the two time-to-event endpoints, missing or incomplete data are managed by standard survival analysis techniques. For patients still on treatment, time on treatment will be censored at the date of data collection. For patients still on treatment and without progression, time to progression will be censored at the date of data collection. For patients stopped treatment and without progression/death or progression/death date missing, time to

progression will be censored on the last contact date.

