9.12 BIAS

Methodological efforts have been taken to minimize selection bias: these efforts include the recommendation to include consecutive patients meeting each of the inclusion criteria and none of the exclusion criteria. In addition, this possible selection bias may be limited by the retrospective aspect of the data collection, data that have been already collected at the time of the study.

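### Patients who started within 6 months of data collection enter only if they have already stopped; by itself this lowers the Kaplan-Meier curves for both time-to-event primary outcomes, by an amount the documents do not fix

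*Protocol*

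**What the plan says.** The exclusion criteria in Protocol section 9.2.1 state: "Patients still on treatment with Gi(l)otrif[®] will be excluded unless treatment period is ≥ 6 months". The abstract repeats the rule: such patients "will be excluded unless treatment period is ≥ 6 months". Section 9.2.1 says the threshold "for patients being still on treatment was chosen to avoid early censoring and enable collection of mature data on ADRs and treatment duration". Patients who stopped before that point are treated differently: those with less than "6 months will be included to avoid bias". No minimum interval between first dose and data collection is set. Nor do the documents say from which date consecutive patients are counted under the cap of 15 per site.

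Section 9.7.1 then carries everyone forward: "Effectiveness analysis will include all patients treated with Gi(l)otrif". Time on treatment and time to progression, both primary outcomes in section 9.3.2.1, are estimated by Kaplan-Meier. The results "will be compared with data from LUX-Lung 3 trial in descriptive manner". Short follow-up is already handled: "For patients still on treatment, time on treatment will be censored at the date of data collection". The SAP section on derived variables repeats the censoring rules and adds no start-date condition.

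Sections 9.9 and 9.12 discuss selection bias but not this mechanism. Section 9.12 says that "this possible selection bias may be limited by the retrospective aspect of the data collection".

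**The concern.** For a patient who started at least 6 months before data collection, the rule does nothing: stopped or not, the patient qualifies. For a patient who started more recently, eligibility depends on the outcome, because only those who have already stopped can enter. The clause that admits early stoppers to avoid bias protects the first group and creates the bias in the second.

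The stated aims do not need such a rule. Administrative censoring of ongoing patients does not bias Kaplan-Meier. A start-date condition would also prevent early censoring and guarantee at least 6 months of potential follow-up.

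At stake are the absolute medians of two primary outcomes, which are to be set beside LUX-Lung 3. No claim is made about ADR percentages, the log-rank contrast between dose groups, or the net bias of the study.

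**Working it through.** The plan gives no bias, power or event figure to reproduce, so the size is explored under stated assumptions.

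**Inputs**
- True median 11.1 months, or 13.6 for common mutations: LUX-Lung 3 progression-free survival in Protocol section 7, used as a stand-in for both outcomes (assumption).
- Start window W in months: 17 (1 Jan 2015, the launch limit in 9.2.1, to 31 May 2016, start of data collection); 32 (EU approval, 25 Sep 2013, to 31 May 2016); 42 (US approval, 12 Jul 2013, to 31 Dec 2016, end of collection).
- Start dates spread evenly over W, or rising linearly from zero (assumption).
- Event times exponential, or Weibull with shape 1.5 (assumption).
- Eligibility judged at data collection (assumption).

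**Formula for time on treatment.** Let e be the share of all starters who began at least 6 months before data collection, and r the share who began within 6 months and have already stopped. Under the protocol's rule nobody is censored before 6 months, so the 6-month estimate is a simple proportion:

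S*(6) = e × S(6) / (e + r)

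After 6 months the hazard is correct, so the later curve is the true one multiplied by S*(6)/S(6).

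**Worked case: exponential, median 11.1, even starts, W = 17**
- λ = ln 2 / 11.1 = 0.06245; S(6) = 0.6875
- e = 1 − 6/17 = 0.6471
- r = [6 − (1 − 0.6875)/0.06245] / 17 = 0.0586
- S*(6) = 0.6471 × 0.6875 / 0.7057 = 0.630
- Median = 6 + ln(0.630/0.5)/0.06245 = 9.71 months, which is 1.39 too short
- Share of the sample that a start-date restriction would remove: r/(e + r) = 8.3%

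**Time-on-treatment medians under the protocol's rule, W = 17 / 32 / 42**

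| Scenario | True 11.1 | True 13.6 | Share removed (true 11.1) |
|---|---|---|---|
| Exponential, even | 9.71 / 10.50 / 10.66 | 12.17 / 12.98 / 13.15 | 8.3 / 3.7 / 2.7% |
| Weibull, even | 10.52 / 10.85 / 10.92 | 13.06 / 13.37 / 13.43 | 5.2 / 2.3 / 1.7% |
| Exponential, rising | 7.98 / 9.83 / 10.19 | 10.37 / 12.29 / 12.67 | 17.7 / 7.6 / 5.5% |
| Weibull, rising | 9.77 / 10.57 / 10.73 | 12.37 / 13.11 / 13.25 | 11.4 / 4.8 / 3.4% |

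Large-sample simulation agrees with the formula.

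**Time to progression.** The direction depends on progression making stopping more likely. With treatment continuing a mean of 3 months beyond progression (true median 11.1), the simulated loss is 0.2–0.6 months (exponential, even), 0.1–0.2 (Weibull, even), 0.4–1.4 (exponential, rising) and 0.1–0.5 (Weibull, rising).

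**Timing of the eligibility decision.** If a site fixes its patient list and confirms eligibility L months later (exponential, even, W = 32), the loss in median time on treatment is 0.60 months at L = 0, 0.40 at L = 3, 0.28 at L = 4, and nil from L = 6.

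**Sampling error for scale.** The 95% half-width of a median from 200 patients (1.96 × its simulated standard deviation) is 1.5–2.9 months under even starts. The bias exceeds sampling error only for exponential times with rising uptake at W = 17.

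**The case against.** The strongest reply is that the effect may be absent or small.

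- *Recent starters may not be sampled.* Counting consecutive patients forward from launch, with 15 per site at regular prescribers, could leave few or none. Eligibility could also be settled late in the 7-month collection window. Both readings are open and both give no bias. The protocol requires neither.
- *The windows are loose.* Section 9.9 says launch to data collection is shorter than 31.6 months, which argues against W = 32 and 42. A pooled 13-country sample is also unlikely to sit wholly at the 17-month floor, where the largest losses arise. This narrows the range but does not remove the bias: at W = 31.6 the four losses (true 11.1, same order as the table) are 0.61, 0.25, 1.29 and 0.53 months.
- *Time to progression may hardly move.* With a mean of 12 months of treatment beyond progression and 20% toxicity stops by 6 months, the median (exponential, even starts) is 10.9 at W = 17 and 11.0 at W = 32, against 11.1. The claim for this outcome is therefore conditional. Death counts as an event in the protocol's definition and ends treatment, which supports the direction.
- *It is mostly within sampling error, and another bias may oppose it.* Both are true. The uneven consent rules for deceased patients (section 9.9) may push the curves up. But a systematic error does not shrink with sample size, and an unquantified opposing bias is no reason to keep an avoidable one.
- *A sensitivity analysis would be enough.* It would reveal whether recent starters exist, but it would leave the affected estimate as the main result when the correction is cheap.

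**Conclusion.** The concern holds. Among recent starters the entry rule selects on the outcome, and nothing in the analysis section corrects for it. For time on treatment the downward direction is certain whenever recent starters are sampled. For time to progression it holds if progression makes stopping more likely, and it stayed downward in every scenario run.

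The size is not determined by the documents, because the start-date distribution, the order in which charts are taken and the eligibility date are unstated. Under the assumptions above, the time-on-treatment median is too short by 0.2–1.4 months with even uptake and 0.4–3.1 with rising uptake (0.2–1.4 and 0.4–3.2 if the true median is 13.6). It is nil if no recent starters enter. The point should be fixed. Confidence is high for the mechanism, not for any one figure.

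**What to change.** In Protocol section 9.7.1 and the SAP, restrict the effectiveness set to patients whose first dose was at least 6 months before the data-collection date on which eligibility was applied at the site, whether or not still on treatment. Define that date identically for stopped and ongoing patients. If abstraction came later, count back from the eligibility date or, if it was not recorded, from the earlier of registration and abstraction. The choice matters. With abstraction 3 months after eligibility (exponential, even, W = 17/32/42), counting back from abstraction leaves medians of 10.06/10.63/10.77, while counting back from eligibility gives 11.10/11.08/11.09. Keep all enrolled patients in the safety set and describe the selection in section 9.9.

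In large-sample simulation of every time-on-treatment scenario in the table, the restriction returns the median to within 0.05 months of the truth (11.08–11.13 and 13.55–13.63).

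The cost is one analysis-set sentence, one flag derived from the start date already collected (baseline.date in the SAP), and one sentence in 9.9. The set loses about 2–8% of patients under even uptake and 3–18% under rising uptake. Of 200 enrolled, 183–197 or 165–193 remain; of 248 (27.5 sites × 9), 227–244 or 204–240. The effectiveness set may therefore fall below 200, but the enrolment target is untouched. At W = 17 with rising uptake, the median is not reached in 2–35% of simulated restricted samples, against 0.1–12% under the current rule.

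If enrolment has not begun, the same start-date condition could instead replace the exclusion criterion in 9.2.1 and the abstract. The same share is then lost from enrolment unless sites below the 15-patient cap can replace it. Enrolling everyone and censoring ongoing patients also removes the bias, but gives up the protocol's aim of mature follow-up.
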